## **2.2      Institutional Review Board/Independent Ethics Committee**

Before study initiation, the investigator must have written and dated approval/favorable opinion from the IRB/IEC for the protocol, consent form, subject recruitment materials (e.g., advertisements), and any other written information to be provided to subjects. The investigator or BMS should also provide the IRB/IEC with a copy of the Investigator Brochure or product labeling information to be provided to subjects and any updates.

The investigator or BMS should provide the IRB/IEC with reports, updates and other information (e.g., expedited safety reports, amendments, and administrative letters) according to regulatory requirements or institution procedures.

## **2.3      Informed Consent**

Investigators must ensure that subjects are clearly and fully informed about the purpose, potential risks, and other critical issues regarding clinical studies in which they volunteer to participate.

In situations where consent cannot be given to subjects, their legally acceptable representatives are clearly and fully informed about the purpose, potential risks, and other critical issues regarding clinical studies in which the subject volunteers to participate.

BMS will provide the investigator with an appropriate (ie , Global or Local) sample informed consent form which will include all elements required by ICH, GCP and applicable regulatory requirements. The sample informed consent form will adhere to the ethical principles that have their origin in the Declaration of Helsinki.

Investigators must:

1. Provide a copy of the consent form and written information about the study in the language in which the subject is most proficient prior to clinical study participation. The language must be non-technical and easily understood.
2. Allow time necessary for subject or subject's legally acceptable representative to inquire about the details of the study.

3. Obtain an informed consent signed and personally dated by the subject or the subject's legally acceptable representative and by the person who conducted the informed consent discussion.
4. Obtain the IRB/IEC's written approval/favorable opinion of the written informed consent form and any other information to be provided to the subjects, prior to the beginning of the study, and after any revisions are completed for new information.
5. If informed consent is initially given by a subject's legally acceptable representative or legal guardian, and the subject subsequently becomes capable of making and communicating his or her informed consent during the study, consent must additionally be obtained from the subject.
6. Revise the informed consent whenever important new information becomes available that is relevant to the subject's consent. The investigator, or a person designated by the investigator, should fully inform the subject or the subject's legally acceptable representative or legal guardian, of all pertinent aspects of the study and of any new information relevant to the subject's willingness to continue participation in the study. This communication should be documented.

The confidentiality of records that could identify subjects must be protected, respecting the privacy and confidentiality rules applicable to regulatory requirements, the subjects' signed ICF and, in the US, the subjects' signed HIPAA Authorization.

The consent form must also include a statement that BMS and regulatory authorities have direct access to subject records.

The rights, safety, and well-being of the study subjects are the most important considerations and should prevail over interests of science and society.

[figure not shown]
### **3 INVESTIGATIONAL PLAN**

#### **3.1 Study Design and Duration**

This is a phase 1/2, dose-escalation, open-label, non-comparative study of nivolumab or nivolumab in combination with ipilimumab in advanced hepatocellular carcinoma subjects with or without chronic viral hepatitis; and a randomized, open-label study of nivolumab vs sorafenib in advanced hepatocellular carcinoma subjects who are naive to systemic therapy.

The study design schematic is presented in [Figure 3.1-1](#).

**Figure 3.1-1: Study Design of CA209040 and Cohorts 1 - 4**

Three etiologic subtypes are included in the Dose Escalation Phase: uninfected HCC subjects, HCV-infected HCC subjects, and HBV-infected subjects.

The first part of the study is the Dose Escalation Phase designed to establish the safety of nivolumab at different dose levels (Section 3.1.3). The maximum dose level for the dose escalation phase is 10 mg/kg in uninfected HCC subjects and 3 mg/kg in HCV and HBV infected HCC subjects, respectively.

**Upon activation of Amendment 4, the Expansion Phase (200 subjects) is designed to generate additional clinical data at specified doses in 4 cohorts (50 subjects per cohort) including uninfected sorafenib naïve/intolerant subjects, uninfected sorafenib progressors (previously referred to as sorafenib failures in Amendment 4), HCV-infected, and HBV-infected subjects. Uninfected, HCV-infected, and HBV-infected subjects will receive a dose of 3 mg/kg Q2 week IV over 60 minutes. Prior to activation of amendment 8, nivolumab infusions were administered**

over 60 minutes in the Dose Escalation Phase and Expansion Phase; however, upon activation of amendment 8 and based on rationale in [Section 1.4.14](#), nivolumab infusions may be given over 30 minutes to align with the infusion times in the 1L Nivolumab vs. Sorafenib Cohort and Nivolumab plus Ipilimumab Combination Cohort.

**Upon activation of Amendment 8**, enrollment into the Expansion Phase will close (if not already completely enrolled), and the 1L Nivolumab vs Sorafenib Cohort will begin accrual. This is an open-label, randomized, cohort in adult (>18 years) male and female subjects with advanced HCC. Subjects must not be amenable for management with surgery or loco-regional therapy. Approximately 130 advanced HCC subjects who are naive to systemic therapy (uninfected, HCV-infected, or HBV-infected) will be randomized 1:1 to receive open label flat dose nivolumab 240 mg Q2 week IV over 30 minutes (Arm A) or sorafenib 400 mg po BID (Arm B) until unacceptable toxicity or RECIST 1.1 radiographic progression or study discontinuation for any other reason ([Section 3.5](#)). Uninfected, HCV-infected, or HBV-infected subjects will be enrolled. Subjects will be stratified by viral status (HCV vs non-HCV [HBV infected or uninfected]) and presence of macrovascular invasion (MVI) or extrahepatic spread (EHS). Subjects with resolved HCV infection will be stratified into the HCV group.

**Upon activation of Amendment 8**, enrollment into the Expansion Phase will close (if not already completely enrolled), and the Nivolumab and Ipilimumab Combination Cohort will begin accrual of up to 120 subjects. Uninfected, HCV-infected, or HBV-infected subjects with advanced HCC and previous treatment with sorafenib will be randomized 1:1:1 into 3 different dose arms:

- Arm A--nivolumab 1 mg/kg + ipilimumab 3 mg/kg q3 week x 4 followed by flat dose nivolumab 240 mg IV q2week until toxicity or disease progression (n = 40)
- Arm B--nivolumab 3 mg/kg + ipilimumab 1 mg/kg q3week x 4 followed by flat dose nivolumab 240 mg IV q2week until toxicity or disease progression (n = 40)
- Arm C--nivolumab 3 mg/kg q2week + ipilimumab 1 mg/kg q6week until toxicity or disease progression (n = 40).

Since the use of nivolumab and ipilimumab has not been previously studied in subjects with advanced HCC, a 2 stage design will be employed for each of the 3 dose arms. In Stage 1, 12 subjects will be enrolled in each dose arm, and will undergo a safety and tolerability assessment at Week 13 (or prior to Week 13 if discontinued) prior to enrollment of any additional subjects.

The safety evaluation ([Section 3.1.4](#)) will be conducted independently for each dose arm in Stage 1 based on criteria described in Discontinuation Criteria ([Sections 4.1.18](#) for nivolumab and [4.2](#) for ipilimumab). No additional subjects will be enrolled until the safety evaluation at Week 13 occurs. Enrollment of the first 12 subjects in each dose cohort will be limited to select sites. After completion of Stage 1, enrollment in Stage 2 of the subsequent 28 subjects can occur in each dose arm and is contingent upon the results of the safety evaluation.

**Number of Subjects:** Approximately 500 subjects including the Dose Escalation Phase (~ 50 subjects), Expansion Phase (200 subjects), 1L Nivolumab vs Sorafenib Cohort (~ 130 subjects), and Nivolumab plus Ipilimumab Combination Cohort (120 subjects).

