**Table 1.4.6-1: Investigator-assessed ORR and Best Overall Response (RECIST v1.1) by Nivolumab Dose - Response Evaluable Subjects - CA209040**

	Nivolumab Dose					
	0.1 mg/kg (N = 6)	0.3 mg/kg (N = 9)	1 mg/kg (N = 10)	3 mg/kg (N = 6)	10 mg/kg (N = 12)	Total (N = 42)a
ORR, number (%) responders	1 (17)	1 (11)	2 (20)	3 (50)	1 (8)	8 (19)
Best overall response, number (%)						
Complete response (CR)	-	-	1 (10)	1 (17)	-	2 (5)
Partial response (PR)	1 (17)	1 (11)	1 (10)	2 (33)	1 (8)	6 (14)
Stable disease (SD)	3 (50)	5 (56)	5 (50)	2 (33)	5 (42)	20 (47)
Progressive disease (PD)	1 (17)	3 (33)	3 (30)	1 (17)	6 (50)	14 (33)

a Five subjects do not have disease assessments as of the database lock on 12-Mar-2015: One subject had death prior to disease assessment, and 4 subjects had recently started the study and were not yet available.

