#### **1.4.14 Rationale for Shorter Infusion Times With 240 mg Flat Dose Nivolumab and Ipilimumab**

Long infusion times place a burden on patients and treatment centers. Establishing that nivolumab and ipilimumab can be safely administered using shorter infusion times of 30 minutes duration in subjects will diminish the burden provided no change in safety profile.

Previous clinical studies of nivolumab monotherapy and ipilimumab monotherapy and the combination of nivolumab and ipilimumab have used a 60 minute infusion duration for nivolumab and 90-minute infusion duration for ipilimumab (1 - 3 mg/kg dosing for both).

However, both nivolumab and ipilimumab have been administered at up to 10 mg/kg with the same infusion duration:

- Nivolumab has been administered safely over 60 minutes at doses ranging up to 10 mg/kg safely over long treatment duration. In Study CA209010, (a Phase 2, randomized, double blinded, dose-ranging study of nivolumab in subjects with advanced/metastatic clear cell RCC) a dose association was observed for infusion site reactions and hypersensitivity reactions (1.7% at 0.3 mg/kg, 3.7% at 2 mg/kg and 18.5% at 10 mg/kg). All the events were Grade 1 - 2 and were manageable. An infusion duration of 30 minutes for 3 mg/kg nivolumab (30% of the dose provided at 10 mg/kg) is not expected to present any safety concerns compared to the prior experience at 10 mg/kg nivolumab dose infused over a 60-minute duration.
- Similarly, ipilimumab at 10 mg/kg has been safely administered over 90 minutes. In the CA184022 study, where ipilimumab was administered up to a dose of 10 mg/kg, on-study drug related hypersensitivity events (Grade 1 - 2) were reported in 1 (1.4%) subject in the 0.3 mg/kg and in 2 (2.8%) subjects in the 10 mg/kg group. There were no drug-related hypersensitivity events reported in the 3 mg/kg group. Across the 3 treatment groups, no Grade 3 - 4 drug-related hypersensitivity events were reported and there were no reports of infusion reactions. Ipilimumab 10 mg/kg monotherapy has also been safely administered as 90 minute infusion in large phase 3 studies in prostate cancer (CA184043) and as adjuvant therapy for stage 3 melanoma (CA184029), with infusion reactions occurring in subjects. Administering 1 mg/kg of ipilimumab represents one-tenth of the 10 mg/kg dose.

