Overall, infusion reactions including high-grade hypersensitivity reactions have been uncommon across nivolumab or ipilimumab clinical studies or the combination of nivolumab and ipilimumab. Furthermore, a 30-minute break after the first infusion for the combination cohort will ensure the appropriate safety monitoring before the start of the second infusion. Overall, a change in safety profile is not anticipated with 30-minute infusion of nivolumab, ipilimumab or combination.

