#### **Treatment Phase:**

Nivolumab monotherapy will be given on an every two week schedule and one treatment cycle (42 days) is comprised of three doses in the Dose Escalation (at doses of 0.1 mg/kg to 10 mg/kg q2week) and Expansion Phase (3 mg/kg q2week). In the 1L Nivolumab vs Sorafenib Cohort, nivolumab monotherapy (240 mg IV) will be given on an every two week schedule with 1 dose = 1 cycle; sorafenib will be given 400 mg po BID. In the Nivolumab plus Ipilimumab Combination Cohort, the dosing will be as outlined above, with no less than 19 days between doses in Arms A and B during the q3week induction phase. In arm C, nivolumab doses may be given no less than 12 days between doses, and ipilimumab doses no less than 5 weeks between scheduled doses

All subjects except those in the 1L Nivolumab vs Sorafenib Cohort will undergo tumor assessments at every q6 week ( $\pm$  2 days) for the first 48 weeks, and then q12 week ( $\pm$  1 week) thereafter until disease progression. Subjects in 1L Nivolumab vs Sorafenib Cohort will undergo tumor assessments q8 week ( $\pm$  1 week) for the first 48 weeks, and then q12week ( $\pm$  1 week) thereafter until disease progression or treatment is discontinued (whichever occurs later). Imaging assessments should be scheduled regardless of dose delay or missed doses in all cohorts.

Prior to activation of Amendment 8, subjects in the Dose Escalation Phase were treated until either a confirmed CR, completion of 2 years of therapy, toxicity, or disease progression. However, upon activation of Amendment 8, all subjects are to be treated until toxicity, RECIST 1.1 defined progression ([Appendix 2](#)), unacceptable toxicity, or study discontinuation for any other reason ([Section 3.5](#)). Treatment may continue beyond progression under protocol defined.

Subjects will continue to receive nivolumab, sorafenib, or nivolumab plus ipilimumab until:

1. RECIST 1.1-defined radiographic progression or unacceptable toxicity.
2. Clinical deterioration ([Section 3.1.4](#)) suggesting that no further benefit from treatment is likely.
3. Meets criteria for discontinuation of study therapy as outlined in [Sections 3.1.3.1](#) (Dose Limiting Toxicity), [3.5](#) (Discontinuation of Subjects from Treatment), [4.1.18](#) (Nivolumab Permanent Discontinuation Criteria), [4.1.12](#) (Treatment Interruption or Discontinuation for Sorafenib Treatment) or [4.2](#) (Ipilimumab Permanent Discontinuation Criteria)

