#### **4.1.3 *Handling and Dispensing***

The product storage manager should ensure that the study drug is stored in accordance with the environmental conditions (temperature, light, and humidity) as determined by BMS. If concerns regarding the quality or appearance of the study drug arise, the study drug should not be dispensed and contact BMS immediately.

Investigational product documentation must be maintained that includes all processes required to ensure drug is accurately administered. This includes documentation of drug storage, administration and, as applicable, storage temperatures, reconstitution, and use of required processes (eg, required diluents, administration sets).

The sites are responsible for procuring IV bags, diluent, and in-line filters.

For details on prepared drug storage and administration of nivolumab and ipilimumab, please refer to the current Investigator Brochures. Details regarding mixing and concentrations of the doses will be detailed in the pharmacy binder.

The unblinded pharmacist will obtain treatment assignment by IVRS and prepare unblinded drug□

Nivolumab is to be administered as an approximately 30 to 60-minute IV infusion for weight based dosing and a 30-minute IV infusion in the arms utilizing the 240 mg flat dose. At the end of the infusion, flush the line with a sufficient quantity of normal saline or dextrose solution.

In the Nivolumab plus Ipilimumab Combination Cohort, ipilimumab is to be administered as an approximately 30-minute IV infusion. At the end of the infusion, flush the line with a sufficient quantity of normal saline or 5% dextrose solution. When both study drugs are to be administered on the same day, separate infusion bags and filters must be used for each infusion. Nivolumab is to be administered first. The nivolumab infusion must be promptly followed by a saline flush to clear the line of nivolumab before starting the infusion. The second infusion will always be ipilimumab, and will start at least 30 minutes after completion of the nivolumab infusion.

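### The optional 30-minute nivolumab infusion has no dose limit, so it permits 10 mg/kg at twice the rate its cited rationale relies on (minor, cheap to fix)

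*Combined protocol and SAP*

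**What the plan says.** Section 3.1 (text under Figure 3.1-1) records that each nivolumab infusion took an hour in both the Dose Escalation and the Expansion Phase until Amendment 8. From then on, with Section 1.4.14 given as the reason, it states that "nivolumab infusions may be given over 30 minutes to align with the infusion times" used in the first-line and combination cohorts. The same text sets the dose-escalation maximum at 10 mg/kg for uninfected subjects and 3 mg/kg for HCV- and HBV-infected subjects.

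Section 4.1.3, the administration instruction, gives an "approximately 30 to 60-minute IV infusion for weight based dosing" and a 30-minute infusion for the 240 mg flat dose. It separates weight-based from flat dosing, but not one weight-based dose from another.

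Section 1.4.14 is headed as a rationale for shorter infusions of the 240 mg flat dose and of ipilimumab. Its nivolumab argument reads "An infusion duration of 30 minutes for 3 mg/kg nivolumab (30% of the dose provided at 10 mg/kg"), and it expects no safety concern relative to 10 mg/kg over 60 minutes. It also reports, from a renal cell carcinoma study, that infusion-site and hypersensitivity reactions rose with dose, adding that "All the events were Grade 1 - 2 and were manageable". It closes with the general statement that "a change in safety profile is not anticipated with 30-minute infusion of nivolumab, ipilimumab or combination".

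Section 3.1.1 (Treatment Phase) states that "upon activation of Amendment 8, all subjects are to be treated until toxicity, RECIST 1.1 defined progression" or discontinuation for another reason. This replaced the earlier stop at confirmed complete response or two years.

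**The concern.** The 30-minute permission is wider than the argument offered for it. It names the whole Dose Escalation Phase, which includes 10 mg/kg, while the safety argument stops at 3 mg/kg. By extension that argument covers lower doses and the roughly equivalent flat dose. At 10 mg/kg it gives no support, because 10 mg/kg over 60 minutes is itself the upper reference point.

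A site following the rule literally could give the highest dose faster than any experience the protocol cites. The case can arise: nivolumab dose reductions are not allowed (Section 4.1.7), so a subject on 10 mg/kg stays there, and Amendment 8 removed the two-year limit. The possible harm is an avoidable infusion reaction. A Grade 3 infusion reaction of any duration requires permanent discontinuation (Section 4.1.18), so the reaction could also cost a benefiting subject the drug.

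**Working it through.** **Inputs**

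- Reference experience: 10 mg/kg over 60 minutes (Section 1.4.14).
- Case argued: 3 mg/kg over 30 minutes (Section 1.4.14).
- Permitted: any weight-based dose over 30 to 60 minutes (Section 4.1.3), with a maximum of 10 mg/kg (Section 3.1).
- Flat dose: 240 mg over 30 minutes (Section 4.1.3); 80 kg reference weight and 35 kg lowest weight in the population PK dataset (Section 1.4.12).
- Reaction rates: 1.7%, 3.7% and 18.5% at 0.3, 2 and 10 mg/kg (Section 1.4.14).
- Best response at 10 mg/kg: Table 1.4.6-1, "Investigator-assessed ORR and Best Overall Response (RECIST v1.1) by Nivolumab Dose".

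**Plan's own figure.** 3 / 10 = 30%, as Section 1.4.14 states. That compares doses. Because the infusion time also changes, the relevant comparison is rate.

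**Rate = dose / time; ratio = rate / (10/60)**

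| Dose (mg/kg) | Time (min) | Rate (mg/kg/min) | Ratio to reference |
|---|---|---|---|
| 10 | 60 | 0.167 | 1.0 |
| 3 | 60 | 0.050 | 0.3 |
| 3 | 30 | 0.100 | 0.6 |
| 5 | 30 | 0.167 | 1.0 |
| 10 | 30 | 0.333 | 2.0 |

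The case argued therefore runs at 0.6 of the reference rate. The permitted extreme runs at 2.0 times the reference and 0.333 / 0.100 = 3.3 times the case argued. Any dose above 5 mg/kg given over 30 minutes exceeds the reference. For an 80 kg subject on 10 mg/kg, the absolute rate rises from 800 / 60 = 13.3 mg/min to 800 / 30 = 26.7 mg/min.

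**Flat dose**

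- 240 / 30 = 8 mg/min.
- At 80 kg: 8 / 80 = 0.100 mg/kg/min, the same as the case argued.
- Weight at which it equals the reference: 8 / (10/60) = 48 kg.
- At 35 kg: 8 / 35 = 0.229 mg/kg/min, 1.37 times the reference.

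**Who could be affected.** At the March 2015 cutoff the 10 mg/kg column shows 1 PR + 5 SD + 6 PD = 12 response-evaluable subjects, so 12 - 6 = 6 did not have progression as best response. This is best response, not treatment status, and Amendment 8 followed in July 2015. It shows that continued 10 mg/kg dosing was possible; it does not estimate how many subjects were affected.

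**The case against.** The strongest reply is that the permission limits itself. Section 3.1 grants it on the basis of Section 1.4.14 and to match cohorts that use only 1 mg/kg, 3 mg/kg or 240 mg flat, so a careful reader would not apply it to 10 mg/kg. This does not succeed. The sentence expressly covers the Dose Escalation Phase, and Section 4.1.3, which sites follow when preparing infusions, carries neither the cross-reference nor a limit.

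Other points stand in part:

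- **Few or no subjects.** No new 10 mg/kg dosing is planned. Nine uninfected subjects had already been treated at that dose by October 2014 (Section 1.1.3), and median time to progression across doses was 4.2 months (Section 1.4.6). The affected group may be empty. This lowers the severity and leaves the rule unchanged.
- **Unseen sources.** Section 4.1.3 refers to the Investigator Brochures for administration details and to the pharmacy binder for mixing and concentrations. A dose-specific time may be given there or in the on-treatment schedules.
- **Dose, not rate.** The 1.7%, 3.7% and 18.5% gradient is by dose. The text available gives no comparison of one dose at two infusion times, so higher risk from the faster rate is an inference. The events were also all Grade 1-2.
- **Existing safeguards.** Section 4.4.1 sets out graded management of infusion reactions, including restart at half the original rate after a Grade 2 interruption. That treats reactions but does not correct the starting rate. For 10 mg/kg over 30 minutes, half the rate is 0.167 mg/kg/min, the reference itself.
- **Light subjects on flat dosing.** A cap on weight-based doses leaves 240 mg over 30 minutes above the reference rate below 48 kg. This is correct, and the sponsor could consider it in the same edit.

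**Conclusion.** The concern holds, as a minor one. The administration rule authorises 10 mg/kg over 30 minutes, at 2.0 times the rate of the experience its rationale relies on and 3.3 times the rate it argues for. The general closing sentence of Section 1.4.14 adds no data at that dose and rate.

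This rests on reading Sections 3.1 and 4.1.3 as written and on no dose-specific restriction appearing in the documents that could not be seen. It matters to subjects only if some remained on 10 mg/kg after Amendment 8, which the protocol does not state. The 30-minute option is permitted, not required. No endpoint, sample size or analysis is affected.

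**What to change.** In Sections 3.1 and 4.1.3, state: *Nivolumab doses of 3 mg/kg or less, and the 240 mg flat dose, may be given over 30 minutes; 10 mg/kg doses are given over 60 minutes.* The fastest weight-based 30-minute infusion is then 3 / 30 = 0.100 mg/kg/min, 0.6 of the reference, and 10 mg/kg stays at the reference rate.

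The cost is one sentence in each of two sections, a check that the pharmacy binder agrees, and 30 minutes more chair time per infusion for any remaining 10 mg/kg subject. Cohorts dosed at 3 mg/kg or less, or at 240 mg flat, are unaffected. While making the edit, the sponsor could also decide whether subjects under 48 kg on the flat dose need a longer infusion, since this wording does not address them.
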